#### **4.1.5 Termination of Study**

This study may be terminated at any time by the principal investigator (PI) in consultation with the CDC and collaborating academic institutions. Otherwise, the study will be terminated at the end of enrollment, analysis, and publication of findings.

## 5 STUDY PROCEDURES

### 5.1 Data Collection

The following endpoints will be collected for analysis in this quality improvement study.

#### **Endpoints**

*Primary endpoint:*

- 1) Antibiotic utilization measured as antibacterial Days of Therapy (DOT) among randomized patients.
  - a. Definitions
    - i. Days of therapy (DOT) is defined as the number of calendar days of antibacterial agent exposure. A DOT is counted for any amount of antimicrobial given on that calendar day. For example, administration of cefazolin as a single dose or as 3 doses given 8 hours apart but within the same 24-hour period both represent 1 DOT. Single agents are counted separately and then summed. For example, administration of vancomycin plus ceftazidime on the same calendar day would represent 2 DOT for the same calendar day.
    - ii. Antibacterial agents will be defined by NHSN AU Module antimicrobial category="Antibacterial" (see Appendix 3). Antibiotics added to the NHSN AU option during the study (e.g. if newly FDA-approved), will be added to the study protocol Table as needed.
      1. "Luminal" antibiotics that do not achieve adequate distribution for treatment of systemic infections will be excluded as follows: oral vancomycin, fidaxomicin, and rifaxamin.
      2. Route of antibacterials will be limited to those identified in the NHSN AU module given by digestive, intravenous, inhaled, or intramuscular.
  - b. Measurement of DOT will start one day after randomization to ensure antibacterial agents given prior to randomization are not included in outcome.
  - c. Measurement will include inpatient DOT plus intended post-discharge antibacterial DOT through 30 days post-randomization.
    - i. Post-discharge antibacterial DOT will be limited to the planned DOT/duration at the time of discharge
    - ii. DOT associated with readmissions during the 30-day post-randomization period will not be included in the primary endpoint, but will be included in measurement of adverse events.

**Table 3. DETOURS Desirability of Outcome Ranking (DOOR) Outcome**

Outcome	Rank
Alive	1
Readmission, relapse of suspected sepsis, C. difficile infection, OR deep venous thrombosis	2
≥2 of items in Rank 2 above	3
Subsequent ICU Admission OR hemodialysis	4
Subsequent ICU Admission AND hemodialysis	5

Death	6
-------	---

*Secondary endpoints:*

- 1) DOOR/RADAR, according to criteria developed in DETOURS-Retro (Pro00076818; Table 3). See Section 7 for definitions of these and other outcomes.
- 2) Safety outcomes potentially related to antibiotic treatments:
  - a. Individual clinical outcome components in the DOOR (Table 3)
  - b. Number of hospital days within 30-days post-randomization
  - c. Re-initiation of antibiotic therapy after >48 hours of no antibiotics within 30-days post-randomization
  - d. Need for new PICC line insertion within 30-days post-randomization
  - e. Central line days within 30-days post-randomization.
- 3) Process indicators:
  - a. Percent of eligible patients with antibiotic de-escalation by day 5, according to an electronic definition of de-escalation
  - b. Of those patients eligible for assessment of de-escalation per the Safety Checklist:
    - i. Number of eligible patients in whom the safety screen was applied.
    - ii. Number patients the safety screen excluded from the opt-out procedure
    - iii. Number of eligible patients in whom the opt-out procedure was employed
    - iv. Number of eligible patients in whom the prescriber chose to opt-out
      1. Prescriber type (e.g. physician, APC, trainee, specialty service consultant (e.g. infectious diseases))
      2. Prescribers' reported rationale for opting out
  - c. Percent of subjects who received an infectious disease consultation after implementation of the Opt-Out
- 4) Days of therapy for specific sub-groups of patients, including patients whose physicians elected to opt-out of the intervention, and sub-groups of hospitals (e.g., community vs. tertiary care hospitals).
- 5) Total days of therapy for each patient, defined as a sum of inpatient days of therapy and projected outpatient days of therapy, as per discharge prescriptions.
- 6) Length of therapy (LOT), defined as the number of days during which the patient receives one or more antibiotics. Repeat primary outcome and secondary outcomes #4 and #5 with LOT.

*Additional Descriptive Data*

We will obtain the following data from each of the patients eligible for the Opt-out protocol:

1. Patient characteristics: age, gender, race, admission and discharge dates, location prior to admission (e.g. transfer from another facility or skilled nursing facility), prior hospitalization in the last 90 days, prior surgery within the last 30 days, ICU admission date (if applicable)
  - a. Length of stay during index admission
  - b. Length of stay prior to enrollment
2. Primary and secondary diagnoses (by ICD-10 code)

3. Methods for implementation of the protocol, including centralized versus de-centralized pharmacist and communication method.
4. Outpatient and/or post-discharge antibiotic exposures in the 30 days post randomization.

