## LIST OF ABBREVIATIONS

CMS	Centers for Medicare and Medicaid
SEP-1	Sepsis Core Measure
NHSN	National Healthcare Safety Network
AUR	Antimicrobial Use and Resistance
Antibiotic	Any medications included in the “antibacterial” category in the NHSN AUR module Appendix 3
Sepsis Bundle	Hospital-specific implementation process that includes the elements of the Surviving Sepsis Campaign’s 3- (includes initiation of broad-spectrum antibiotics) and 6- hour bundle used to evaluate SEP-1 Core Measure compliance
Opt-Out Procedure	Hospital-specific implementation process for the designated pharmacist to notify an ordering prescriber that patient meets DETOURS criteria for antibiotic de-escalation.

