## 7 ASSESSMENT OF SAFETY

All randomized patients will undergo safety evaluation.

1. Specifications of safety parameters –Data will be collected on the adverse outcomes described in the Desirability of Outcome Ranking (DOOR) in Table 3 and three other safety outcomes:
  - a. C. difficile infection (CDI) – positive *C. difficile* stool test during the 30 days following randomization. Results from either PCR or ELISA tests are acceptable
  - b. Clinically significant deep venous thrombosis (DVT) – diagnosis of a new DVT during the 30 days following randomization that requires anticoagulation. A radiographic finding (via ultrasound, CT, or MRI) will be required for this diagnosis.
  - c. Readmission – return to the hospital within 30 days of hospital discharge
  - d. Relapse of suspected sepsis – restart or escalation of antibiotic therapy coupled with repeat blood cultures (+/- 24 hours of changed in antibiotic therapy) during the 30 days following randomization.
  - e. Acute kidney injury requiring hemodialysis – new onset acute kidney injury requiring 1 or more hemodialysis sessions during the 30 days following randomization.
  - f. Transfer to Intensive Care Unit (ICU) – admission or transfer to any intensive care unit within 30 days of randomization.
  - g. Death – within 30 days of randomization.
  - h. Number of hospital days (Length of Stay) starting on the day of randomization and up to 30 days post randomization.
  - i. Re-initiation of antibiotic therapy after >48 hours of no antibiotics within 30 days of randomization.
  - j. Need for new PICC line insertion within the 30 days of randomization.
2. Methods and timing for assessing, recording, and analyzing safety parameters – Local study personnel will be responsible for assessing and recording safety parameters. Duke study personnel will be responsible for monitoring safety through interaction with study site PIs and the Independent Monitor.
3. Guidelines for determining causality – causality will not be assessed, as the DOOR outcome is intended to reflect global patient outcomes.
4. Reporting procedures (for AE) – all safety parameters will be entered into the REDCap database. Data on safety parameters will be reviewed by the Independent Monitor and discussed with the central study team.

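### The luminal-antibiotic exclusion is stated only for the primary endpoint, so C. difficile treatment can be classified as re-initiation or sepsis relapse (minor)

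*Protocol*

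**What the plan says.** The protocol's List of Abbreviations gives a document-wide meaning for antibiotic: "Any medications included in the “antibacterial” category in the NHSN AUR module Appendix 3". The Appendix 3 table lists fidaxomicin as antibacterial. It also lists vancomycin as antibacterial, without a route.

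Section 5.1, primary endpoint, item a.ii uses the same NHSN category to say which agents count towards days of therapy (DOT). Its first sub-item then removes luminal agents: "antibiotics that do not achieve adequate distribution for treatment of systemic infections will be excluded as follows: oral vancomycin, fidaxomicin, and rifaxamin". That exclusion appears nowhere else.

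Three other outcomes depend on what an antibiotic is:

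- **Re-initiation** (Section 5.1 item 2c): "Re-initiation of antibiotic therapy after >48 hours of no antibiotics within 30-days post-randomization". Section 7 item 1.i and Appendix 4 repeat it in nearly the same words.
- **Relapse of suspected sepsis** (Section 7 item 1.d and Appendix 4): "restart or escalation of antibiotic therapy coupled with repeat blood cultures", with the cultures within 24 hours of the change.
- **Length of therapy, LOT** (Section 5.1 item 6): "defined as the number of days during which the patient receives one or more antibiotics". The same item then says that the primary outcome is to be repeated using LOT.

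In Table 3, C. difficile infection and relapse are separate rank 2 items, and two or more rank 2 items give rank 3.

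**The concern.** The reason given for excluding luminal agents from DOT is that they do not reach systemic infections. By the same reasoning, starting such an agent is not evidence that systemic treatment had to restart or that sepsis relapsed. Yet the only definition of antibiotic that reaches re-initiation and relapse brings oral vancomycin and fidaxomicin in. This is a stated rule that sorts some events wrongly, rather than a detail left for later.

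Two kinds of error follow. C. difficile treatment may be recorded as a re-initiation and, with cultures, as a relapse, so the same episode enters DOOR twice. In the other direction, luminal treatment may keep a patient from ever reaching the antibiotic-free interval, so a real systemic restart goes unrecorded.

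At stake are a descriptive safety outcome, the Independent Monitor's table in Appendix 4 (which shows C. difficile, sepsis relapse and re-initiation together by arm) and a small part of the DOOR comparison.

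**Working it through.** The protocol gives no figure to reproduce here. The check applies the definitions as written, then bounds the number of patients affected.

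**1. Which agents count.** Under the List of Abbreviations with Appendix 3, oral vancomycin and fidaxomicin are antibiotics. Under Section 5.1 item a.ii.1 they are not counted. The route limit in a.ii.2 does not settle the matter, because the digestive route is allowed. Rifaximin is not in the printed Appendix 3 table, so the conflict concerns the other two agents.

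**2. False re-initiation.** Systemic antibiotics stop at randomization and oral vancomycin for C. difficile runs on days 12-21. As written, more than 48 hours passed without antibiotics and one was then started: re-initiation, yes. With luminal agents excluded: no.

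**3. Missed re-initiation.** Systemic antibiotics stop at randomization, oral vancomycin runs on days 2-11, and cefepime starts on day 13, no more than 48 hours after the last vancomycin dose. As written, there was never a gap of more than 48 hours: re-initiation, no. With luminal agents excluded, the gap runs from randomization to day 13: yes.

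**4. Double count in DOOR.** Take the patient in step 2 and add repeat blood cultures within 24 hours of starting oral vancomycin. The restart and the cultures together meet the relapse definition. C. difficile plus relapse makes two rank 2 items, so rank 3. With luminal agents excluded, C. difficile is the only item, so rank 2. (This assumes no other DOOR event.)

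**5. Number of patients.** Assumptions: 30-day C. difficile in 1-3% of patients, all treated with a luminal agent.

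- Cases: 762 × 0.01 = 7.6 to 762 × 0.03 = 22.9, or about 8-23. This is the upper bound before any further condition.
- False re-initiations, if 50-100% start after the gap: 7.62 × 0.5 = 3.8 to 22.86 × 1.0 = 22.9, or about 4-23.
- Moves from rank 2 to rank 3, if 20-50% of those also have cultures in the window: 3.81 × 0.2 = 0.8 to 22.86 × 0.5 = 11.4, or about 1-11.

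**6. Effect on DOOR.** Put all 11.4 moves in one arm of 762 / 2 = 381, and assume that 30% of the other arm is in ranks 2-3. Only comparisons with those patients can change. The probability of a better outcome then shifts by at most 11.4 / 381 × 0.30 = 0.009.

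**7. Direction between arms.** Let *t* be the true re-initiation rate, *c* the C. difficile rate and *g* the fraction starting after the gap. With independence, the reported rate is t + cg − t·cg. Take t = 10% (intervention) and 8% (control), a true excess of 2.0 points.

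- c = 1% vs 3%, g = 75% in both arms: 0.10 + 0.0075 − 0.00075 = 10.7%, and 0.08 + 0.0225 − 0.0018 = 10.1%. The excess shrinks to about 0.6 points.
- c = 2% in both arms, g = 100% vs 50%: 0.10 + 0.02 − 0.002 = 11.8%, and 0.08 + 0.01 − 0.0008 = 8.9%. The excess grows to about 2.9 points.

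The sign depends on inputs that the protocol does not give.

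**The case against.** The best defence is that there is only one agent list. The exclusion sits in item a.ii, which says what antibacterial agents are, and not in the counting rule a.i. The List of Abbreviations points to the same NHSN category, so a.ii may be read as its working form. Item c.ii adds that DOT from readmissions enters the measurement of adverse events, which hints that the DOT rules were meant to reach safety outcomes. Section 5.1 also promises a data dictionary for all outcomes, Section 9.4.1 defers detail to the SAP, and Appendix 4 has events found by chart review with site investigators looking at each one. A sensible abstractor would often not call oral vancomycin a restart.

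This lowers the likely damage but does not remove the conflict. No sentence carries the exclusion to re-initiation or relapse, and the document-wide definition points the other way. The SAP is due only before database lock, whereas local staff at a projected ten hospitals record these events throughout, and the Independent Monitor sees them at 10%, 25% and 50% of enrollment.

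Two stronger readings are tempting, and the protocol supports neither.

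- **That luminal days are added to LOT, so that LOT could exceed DOT.** Item 6 tells the analyst to repeat the primary outcome with LOT. That most naturally brings over the primary endpoint's agent list and its window, in which post-discharge days count only as planned at discharge and readmission days are left out. This is at most an ambiguity.
- **That the false counts fall mainly on controls and hide harm from stopping antibiotics.** The secondary hypothesis expects less C. difficile in the intervention arm, but antibiotic-free gaps should be more common there. The two pull in opposite directions.

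**Conclusion.** The point holds for re-initiation and for relapse, each under its own condition: a gap of more than 48 hours for the first, and a restart or escalation with repeat blood cultures within 24 hours for the second. As written, C. difficile treatment can be counted as either, one episode can be ranked 3 instead of 2 in DOOR, and a true systemic restart can be missed.

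The severity is minor. The figure of about 8-23 exposed patients rests on an assumed C. difficile rate of 1-3% and on every case receiving a luminal agent. The protocol defines C. difficile by a positive stool test alone, so some cases may not be treated that way. Re-initiation is only summarized descriptively. The DOOR shift of at most 0.009 rests on extreme allocation and on an assumed 30% of the other arm in ranks 2-3. Nothing can be said about which arm gains, and the primary endpoint is unaffected because its own definition already excludes these agents.

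**What to change.** In Section 5.1 item 2c, Section 7 items 1.d and 1.i, and the matching Appendix 4 definitions, state that antibiotic means the agents and routes counted for the primary endpoint in Section 5.1 item a.ii, with luminal agents excluded. Starting, stopping or being on a luminal agent is then neither a restart nor an escalation and does not interrupt the 48-hour interval. C. difficile and its treatment are counted once, as the C. difficile component. Add a cross-reference at the entry in the List of Abbreviations. For LOT, simply confirm that the same agent list applies.

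The cost is one sentence and the matching entry in the data dictionary, because the agent and route filter is already needed for DOT. Re-initiation and relapse counts will probably be slightly lower. Safety events already recorded by sites should be checked once against the clarified definition.

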## 9.4 Analysis Plan

### 9.4.1 Analysis

Descriptive data will be summarized by treatment group and overall using standard statistical methods. Full details of the planned analyses will be specified in a statistical analysis plan (SAP) which will be completed prior to the database lock.

*Primary analyses*

The primary outcome (antibiotic DOT) will be evaluated using GEE negative binomial regression with treatment as the only covariate, hospital as the cluster variable and assuming compound symmetry covariance structure within the clusters. Model fit will be examined and alternative distributions for the regression model (Poisson or overdispersed Poisson) may be considered.

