### *Secondary analyses*

Secondary outcome #1 (RADAR/DOOR) will be compared between treatment arms using Wilcoxon rank-sum test. Probability of a better RADAR/DOOR for a randomly selected patient using DETOURS strategy compared with control will be calculated, along with the 95% confidence interval.

Safety outcomes (secondary outcome #2) and process indicators (secondary outcome #3) will be analyzed using summary statistics.

Secondary outcomes including DOT and LOT (secondary outcomes #4, #5, and #6) will be analyzed using the same method as for the primary outcome #1 above.

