### *Analysis populations*

Intent-to-treat (ITT) population will include all randomized patients. Patients will be analyzed as randomized.

Per-protocol (PP) population will consist of all randomized patients without major inclusion/exclusion criteria violations, which will be pre-defined in the SAP. Patients will be analyzed as treated.

Primary and key secondary analyses will be performed both in the ITT and PP populations; all other analyses will be performed in the ITT population only.

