### *Subgroup analyses*

Subgroup analyses of the primary outcome will evaluate whether the treatment effect is consistent between 1) medicine patients vs. surgical patients 2) between study hospitals and 3) comparing academic to community hospitals. Additional analyses will compare differences in outcomes and patient/prescriber characteristics for patients in whom protocol-driven de-escalation was implemented versus those in whom the prescriber opted-out of de-escalation. Process indicators for these subgroups will be analyzed using summary statistics.

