## **15 QUALITY CONTROL AND QUALITY ASSURANCE**

The principal investigator will ensure that all study personnel are appropriately trained and applicable documentations are maintained. QC strategies for data transmission are already in place.

Site PIs will assign the task of QC/QA checks to a local study monitor. The study monitor will evaluate appropriate application of the safety check criteria by sampling 15-20% of enrolled patients and confirming presence or absence of the safety check criteria to confirm fidelity to protocol.

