## **PLAN FOR DATA MANAGEMENT**

Compliance of regulatory documents and study data accuracy and completeness will be maintained through an internal study team quality assurance process. Site PIs will assign the task of Quality Control/Quality Assurance checks to a local study monitor. To ensure the screening processes, as implemented at individual study sites, are adequately selecting the intended low-risk population for de-escalation procedures, the safety criteria will be confirmed retrospectively. The study monitor will evaluate appropriate application of the DETOURS safety check criteria for all enrolled patients at their planned 30-day post-enrollment assessment of study outcomes. This review will retrospectively confirm the presence or absence of the safety check criteria and therefor confirm fidelity to the screening protocol.

Additionally, study outcome measurement will be confirmed by requesting securely collected screenshots from the electronic health record for a random 10% sample of enrolled patients during the first month of study start at each site. The local study monitor will collect the data during their 30-day chart reviews, and the data will be reviewed by a member of the central study team to confirm the method by which outcomes are assessed. Confirmation of measurement of the primary outcome from the sampled patients will be compared to the electronic data file capture of antibiotic days for study patients.

Confidentiality throughout the trial is maintained by use of a secured data collection tools, data transfer procedures, and a plan to destroy identifiers at the earliest opportunity.

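### Days of therapy in opted-out patients is assigned to the primary treatment-effect model, but opting out happens only in the intervention arm, so that model has no contrast to estimate

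*Protocol*

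**What the plan says.** Protocol Section 5.1, secondary endpoints, item 4 asks for "Days of therapy for specific sub-groups of patients, including patients whose physicians elected to opt-out of the intervention", together with subgroups of hospitals such as community and tertiary care. Item 6 repeats item 4 with LOT in place of DOT.

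Section 9.4.1, Secondary analyses, fixes the method: "secondary outcomes #4, #5, and #6) will be analyzed using the same method as for the primary outcome #1 above". Under Primary analyses, that method is described thus: the outcome "will be evaluated using GEE negative binomial regression with treatment as the only covariate, hospital as the cluster variable".

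The same section touches opt-out status, or could do so, in two more places. Subgroup analyses adds a comparison of outcomes and characteristics for "patients in whom protocol-driven de-escalation was implemented versus those in whom the prescriber opted-out of de-escalation". Analysis populations defines the per-protocol set by the absence of major eligibility violations and then says "Patients will be analyzed as treated", whereas the ITT population is analysed by randomised arm.

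Section 4.1.4 gives the order of events. Randomisation is Step 3, the opt-out approach to the prescriber is Step 4, and the guided discussion after an opt-out is Step 5. Controls receive standard care and have no contact with the study team. Section 5.1, Data Collection Strategy and Sources, has the Step 4 result entered only for patients randomised to intervention.

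**The concern.** A treatment effect within a subgroup needs patients from both arms, and the subgroup should be defined by something that the arm cannot influence. Hospital type meets both conditions. Opt-out status meets neither: it is a reaction to the intervention, it follows randomisation, and no control patient can have it. The protocol names both the subgroup and the model, and the two do not fit together, so this is more than a detail left to the SAP.

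An analyst told to follow the text would have to improvise. The obvious substitute is to compare opted-out patients with all controls. That sets patients whose prescribers judged that antibiotics should continue against an unselected arm, and a ratio from the primary model could be read as a treatment effect. At stake is the interpretation of one named secondary outcome and its LOT repeat. The main result is not at stake.

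**Working it through.** **1. The plan's own figure.** The only computed figure nearby is the power in Section 9.1: 87% for a 25% reduction with 762 patients. It belongs to the ITT primary analysis. It was checked by 500 simulated trials with the Section 9.1 inputs (mean 11.4, scale 1.68, hospital variance 0.12, the ten hospital sizes of Table 4), assuming a two-sided 5% test because no alpha is stated. The result was 87.0%. The closed form with 762/2 = 381 per arm is close: SE = √[(1/11.4 + 1/8.55 + 2 × 1.68)/381] = 0.0967, |ln 0.75| = 0.2877, and Φ(0.2877/0.0967 − 1.96) = 84.5%. The protocol gives no figure for the opt-out subgroup.

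**2. Can the model be fitted inside the subgroup?** The design matrix has two columns, intercept and treatment. Among opted-out patients treatment is 1 for everyone, so the columns are identical and the rank is 1 of 2. No treatment coefficient exists. The same holds for LOT.

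**3. Opted-out patients against all controls.** Assume that neither Step 4 nor Step 5 changes anyone's DOT. Let u be the expected DOT of opted-out patients relative to the average randomised patient. Randomisation puts the control mean at that average, so

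ratio = (u × control mean) / control mean = u.

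- u = 1.2: 13.68 / 11.4 = 1.20
- u = 1.3: 14.82 / 11.4 = 1.30

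Both lie above 1, so a protocol that does nothing would appear to increase antibiotic use in this group.

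**4. A check that does not fix u by hand.** One million patients were simulated with gamma frailty (dispersion 1.68) and no intervention effect. The decision to opt out was correlated with underlying DOT on a latent normal scale. The entries are opted-out patients over all controls:

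| Opt-out share | Correlation 0 | 0.2 | 0.5 |
|---|---|---|---|
| 30% | 1.00 | 1.26 | 1.71 |
| 50% | 1.00 | 1.18 | 1.44 |
| 70% | 1.00 | 1.10 | 1.24 |

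The ITT ratio is 1.00 throughout. The shares and correlations are assumptions; the protocol gives neither.

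**5. Accepted against opted-out patients (Subgroup analyses).** This can be computed, because both groups lie within the intervention arm, but it is not randomised. With opt-out share p, the accepted patients' relative mean under no effect is (1 − pu)/(1 − p). At p = 0.5 this is 0.80 for u = 1.2 and 0.70 for u = 1.3. The ratios to opted-out patients are then 0.80/1.2 = 0.67 and 0.70/1.3 = 0.54.

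**6. The as-treated rule on one possible reading.** If opted-out patients were moved to control, the control mean would become (1 + pu)/(1 + p). At p = 0.5 that is 1.6/1.5 = 1.067 for u = 1.2 and 1.65/1.5 = 1.10 for u = 1.3. The ratios under no effect would be 0.80/1.067 = 0.75 and 0.70/1.10 = 0.64. If opted-out patients stay in the intervention arm, this bias does not arise.

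**The case against.** The strongest reply is that this is one clause in a list of secondary outcomes. The ITT primary analysis, the sample size and the power do not depend on it, and the hospital subgroups in the same item are sound. That stands, and it limits the severity. It does not rescue the clause, because the model for outcome 4 is stated and fails for this subgroup.

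Several stronger readings are tempting and are not supported:

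- **The plan manufactures a large apparent benefit.** A reader might infer this from the 0.70 to 0.80 ratios of accepted patients to all controls in step 5. No section plans that comparison. Item 4 concerns opted-out patients, and against controls their bias runs the other way.
- **The per-protocol analysis has the same flaw.** That set is defined by eligibility violations, and opting out is not one. Section 4.1.4 describes the intervention as the Opt-Out Procedure itself, so a patient whose prescriber was approached and declined has received it. Both groups exist, so the model can be fitted. The bias in step 6 needs treated to mean that antibiotics were stopped, a reading that item 4's wording about opting out of the intervention permits but does not state.
- **The quality-control mismatch undermines the per-protocol set.** Section 15 speaks of "sampling 15-20% of enrolled patients and confirming presence or absence of the safety check criteria", while Appendix 4 says "The study monitor will evaluate appropriate application of the DETOURS safety check criteria for all enrolled patients". These do conflict and should be reconciled. They concern the safety check, however, whereas the inclusion and exclusion criteria of Section 4.1.2 are culture result, broad-spectrum therapy and ICU location. The protocol does not tie per-protocol membership to this audit, so it is a separate matter.
- **The accepted versus opted-out comparison is illegitimate.** It is listed among additional analyses and makes no treatment-effect claim. Describing who opted out and what followed is reasonable if labelled as such. The promise of summary statistics in that paragraph covers only process indicators, so a label is needed.

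**Conclusion.** Wrong as written, minor to should-fix. For opted-out patients, secondary outcome 4 and its LOT repeat in item 6 are assigned a model that cannot estimate a treatment effect. This follows from the protocol's own text and needs no assumption.

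The size of the bias against all controls does rest on assumptions. It is 1.2 to 1.3 if opted-out patients would have had 20% to 30% more DOT, and 1.10 to 1.71 over the simulated range. It vanishes if opting out is unrelated to expected DOT. Some relation is plausible, because a prescriber who opts out has chosen to continue antibiotics, but the protocol does not quantify it. Where it exists in this direction, it counts against the intervention.

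The as-treated rule is ambiguous and has not been shown to be biased. The primary conclusion of the trial is not threatened.

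**What to change.** - In Section 9.4.1, Secondary analyses, limit the primary model for outcome 4, and for its LOT repeat in item 6, to subgroups defined at baseline, such as community and tertiary care hospitals.
- Report DOT and LOT after opt-out descriptively, within the intervention arm only.
- In Subgroup analyses, label the comparison of accepted with opted-out patients as non-randomised and descriptive.
- In Analysis populations, analyse the per-protocol set as randomised, or state that an opted-out patient has received the intervention (the Opt-Out Procedure) and stays in that arm.

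A complier-average estimate, dividing the ITT difference by the acceptance proportion, is not a good substitute. It requires that assignment leave DOT unchanged in opted-out patients. Step 5 (Section 4.1.4 and Appendix 2) is meant to influence them: it encourages narrower treatment, offers changes to orders or stop dates, and prompts reassessment. The scaling would credit any Step 5 effect to accepted patients.

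The cost is a few sentences in the protocol or SAP before database lock. No new data are needed, since the opt-out result is already collected for every intervention patient, and the sample size does not change.
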